 - In-hospital diagnostic testing: left ventricular ejection fraction (based on transthoracic echocardiogram), coronary angiography results (number of vessels involved / % stenosis), PCI details (number and type of stents used, vessel treated).
 - Demographic data: sex, race, ethnicity, insurance status.
 - Physical examination and vital signs: height, weight, and BP.
- *Research Coordinator Assessment*. Procedures listed below will be electronically administered using standardized instruments on a secure, portable tablet computer using a REDCap portal. NYU DataCore will facilitate development of REDCap portal and secure transfer of collected data elements.
 - Additional demographic data: Marital status, education level.
 - Short Form 12 (SF-12) questionnaire.
 - Seattle Angina Questionnaire 7 (SAQ-7).
 - Activities of Daily Living (ADLs).
 - Goal Attainment Scaling. Research Coordinators will guide participants in setting 1 personal goal related to improving daily function or symptom control (e.g., walking with less dyspnea, attending family functions) to achieve over the next 3 months.
 - Mini-Cog screening instrument.
 - Depressive symptoms (PHQ-8).
 - Frailty elements. Unintentional weight loss (≥ 10 pounds in past 1 year), weak grip strength (measured by handheld dynamometer), exhaustion (measured by two questions from CES-D scale), and slow gait (measured in meters/second over a 15-foot walk).
- *Research Nurse Assessment*. The 6 Minute Walk Test (6MWT) is to be performed by a blinded research nurse (to measure 6MWD) following the assessment listed above. Randomization occurs after performance of 6MWT, so that patients with safety issues are excluded (as described under “potential risks”, we anticipate such issues to be relatively rare). The research coordinator will alert the research nurse when the participant is enrolled and introduce the participant for 6MWT. After administering 6MWT (using standardized recommendations from the American Thoracic Society), the research nurse will complete a 6-minute Walk Test Worksheet to document what happened during the session. These forms will be periodically reviewed by the Project Coordinator.

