- *3-month ambulatory assessment (all participants).* The research coordinator will schedule an ambulatory visit to take place 3 months after the baseline assessment. For NYU patients, this visit will occur at a designated research space in the main hospital campus (NYU Tisch Hospital). For participants at NYULH-Winthrop, the visit will be performed at the outpatient office of the FGP of Winthrop Cardiology Associates located at [name]. For UMMHC patients, this visit will take place at the Ambulatory Care Center (1st floor) at [name]. For participants at the Bellevue site, the CTSI Bellevue research suites or designated areas in the NYU main hospital campus will be used. For Yale patients, this visit will take place at ambulatory space adjacent to Yale-New Haven Hospital. The estimated time for the 3-month visit is 1 hour. Measures at 3 months will include a repeat of several baseline instruments to evaluate change over time (weight, BP, SF-12, SAQ-7, ADLs, PHQ-8). Participants will also be asked about hospital readmissions since time of last visit. 6MWT and Goal Attainment Scaling will be performed by the research nurse and/or a blinded assessor.

The Fitbit, portable tablet computer, and BP cuff will be collected. The research coordinator will also perform chart abstraction at 3-months to evaluate ambulatory CR attendance, and to verify self-report of hospital readmissions. For readmissions that occur outside the NYU, Bellevue, UMass or Yale systems, hospital records will be obtained.

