7.2.2 Enrollment/Baseline

Enrollment/Baseline Visit (Visit 1, Day 1)

- Obtain informed consent of potential participant verified by signature on study informed consent form.
- Verify inclusion/exclusion criteria.
- Obtain demographic information, medical history, medication history, comorbidities, and laboratory/cardiac test results.
- Obtain height and weight.
- Record blood pressure.
- Administer study assessments:
 - 6-minute walk test. Standard protocol including vital signs measurement pre- and post-testing.
 - Frailty elements: Unintentional weight loss (≥ 10 pounds in past 1 year), weak grip strength (measured by handheld dynamometer), exhaustion (measured by two questions from CES-D scale), slow gait (measured in meters/second over a 15-foot walk), and low physical activity (measured by kilocalories per week expended).
- Conduct questionnaires:
 - SF-12
 - SAQ-7
 - ADLs
 - Mini-Cog
 - PHQ-8
 - GAS
- (Intervention Participants only):
 - Provide participants with tablet computer
 - Receive FitBit wearable activity monitor and BP cuff monitor
 - Education on cardiac risk factor management (in person or remote)
 - Ascertainment of home environment and barriers to mobility (in person or remote)
 - Introduction to the mHealth-CR software
 - Personalized exercise plan: Participants will be instructed by the exercise therapist to use mHealth-CR for at least 5/7 days each week. Training will include education on BP cuff use.
- All participants will be instructed to participate in phone calls with the research coordinator to complete ADL assessments.

CONFIDENTIAL

This material is the property of the NYU School of Medicine and Langone Medical Center. Do not disclose or use except as authorized in writing by the study sponsor

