7.2.4 Final Study Visit

3-month Ambulatory Visit (Visit 2, Day 90 +30 days)

- Record adverse events as reported by participant or observed by investigator.
- Collect all study devices: tablet computer, FitBit, blood pressure cuff monitor
- All study activities to be performed during the final visit have been detailed in Table in Section 7.1.1.
- In order to minimize bias during the GAS assessment, GAS will be conducted by a blinded assessor at this visit.
- Every effort will be made to complete the 3-month visit at or as close to day 90 as possible.

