Masking. To minimize bias and ensure safety, 6MWT will be performed by a blinded research nurse or blinded exercise therapist unaffiliated with the study intervention. The 6MWT will be performed during baseline hospitalization and at the 3-month follow-up visit. Designating a blinded research nurse serves two purposes: first, since the research coordinator will know the participant's study assignment at 3 month follow-up, a blinded research nurse will reduce the potential for measurement bias (e.g. no differential encouragement in the intervention arm). Second, having a nurse perform the assessment ensures optimal monitoring of potential safety issues (e.g. unsteady gait, lightheadedness) that may warrant cessation of the test. The research coordinator will alert the research nurse when the participant is enrolled and introduce the participant for 6MWT. The research nurse, after administering 6MWT (using standardized recommendations from the American Thoracic Society) will inform the research coordinator of the result, which the coordinator will then enter into REDCap.

CONFIDENTIAL

This material is the property of the NYU School of Medicine and Langone Medical Center. Do not disclose or use except as authorized in writing by the study sponsor

We do not plan to unmask the blinded 6MWT assessor as this may interfere with integrity of the study randomization. We anticipate that adverse events during 6MWT will be very rare, and if they occur, it will not be necessary for the assessor to know the participants' treatment assignment.

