10.6.3 Breaking the Study Blind/Participant Code

There are no plans to unmask the blinded research nurse/6MWT assessor at any time. No other study staff or participants will be blinded.

11 Source Documents and Access to Source Data/Documents

Source data is all information, original records of clinical findings, observations, or other activities in a clinical trial necessary for the reconstruction and evaluation of the trial. Source data are contained in source documents. Examples of these original documents, and data records include: hospital records, clinical and office charts, laboratory notes, memoranda, subjects' diaries or evaluation checklists, pharmacy dispensing records, recorded data from automated instruments, copies or transcriptions certified after verification as being accurate and complete, microfiches, photographic negatives, microfilm or magnetic media, x-rays, subject files, and records kept at the pharmacy, at the laboratories, and at medico-technical departments involved in the clinical trial.

The study case report form (CRF) is the primary data collection instrument for the study. All data requested on the CRF must be recorded. All missing data must be explained. If a space on the CRF is left blank because the procedure was not done or the question was not asked, write "N/D". If the item is not applicable to the individual case, write "N/A". All entries should be printed legibly in black ink. If any entry error has been made, to correct such an error, draw a single straight line through the incorrect entry and enter the correct data above it. All such changes must be initialed and dated. DO NOT ERASE OR WHITE OUT ERRORS. For clarification of illegible or uncertain entries, print the clarification above the item, then initial and date it.

Access to study records will be limited to IRB-approved members of the study team. The investigator will permit study-related monitoring, audits, and inspections by the IRB/EC, government regulatory bodies, and University compliance and quality assurance groups of all study related documents (e.g. source documents, regulatory documents, data collection instruments, study data etc.). The investigator will ensure the capability for inspections of applicable study-related facilities (e.g. pharmacy, diagnostic laboratory, etc.).

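### No blinded person is assigned grip strength and the 15-foot walk at 3 months, so two of the five frailty criteria appear to fall to a coordinator who knows the arm

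*Combined protocol and SAP*

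**What the plan says.** - **Who takes the frailty measurements.** Section 7.1.1 has one block of procedures for the research coordinator and another for the research nurse. The frailty elements are in the coordinator's block: unintentional weight loss, then "weak grip strength (measured by handheld dynamometer), exhaustion (measured by two questions from CES-D scale), and slow gait (measured in meters/second over a 15-foot walk". The 6MWT is in the nurse's block.
- **When.** Table 1 marks the frailty elements for all participants at baseline and at the ambulatory follow-up. Section 10.4.11 also measures frailty at both times.
- **What the coordinator knows.** Section 10.6.1 states that "the research coordinator will know the participant's study assignment at 3 month follow-up". It gives this as a reason for using someone else for the 6MWT: "a blinded research nurse will reduce the potential for measurement bias (e.g. no differential encouragement in the intervention arm").
- **Who is blinded at 3 months.** Section 7.1.1: "6MWT and Goal Attainment Scaling will be performed by the research nurse and/or a blinded assessor". Section 7.2.4 adds that "GAS will be conducted by a blinded assessor at this visit", to limit bias. Section 10.6.3, after naming the nurse or 6MWT assessor, says "No other study staff or participants will be blinded".
- **The endpoint.** Change in frailty status is ancillary (3.2, 4.2.3). Section 10.4.11 classes a participant as frail on 3 of 5 criteria and counts those in each arm who leave the frail category by 3 months.
- **The list of items.** The coordinator's list in 7.1.1 has four elements. Section 7.2.2 has a fifth after gait: "slow gait (measured in meters/second over a 15-foot walk), and low physical activity (measured by kilocalories per week expended"). Sections 4.2.3 and 10.4.11 also name five.

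**The concern.** The plan identifies a source of bias (a tester who knows the arm and may encourage one group more) and protects the 6MWT from it. Grip on a dynamometer and a timed short walk are also performance tests given by a person who instructs the participant, yet they get no such protection at follow-up.

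The baseline assessment comes before randomization, so knowledge of the arm can act only at 3 months and does not cancel out of the change. If encouragement were stronger in the intervention arm, it would produce extra moves out of frailty there, which is the direction section 10.4.11 anticipates. At stake is the interpretation of one ancillary comparison.

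**Working it through.** The plan gives no figure to reproduce. The check is a side-by-side reading, followed by a count of how far the frailty classification depends on the two tests.

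**1. Assessor at each visit**

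| Measure | Baseline | 3 months | Blinded at 3 months? |
|---|---|---|---|
| 6MWT | Research nurse or independent therapist (7.1.1) | Same (7.1.1, 10.6.1) | Yes |
| GAS | Coordinator guides goal setting (7.1.1) | Nurse or blinded assessor (7.1.1, 7.2.4) | Yes |
| Grip, 15-foot walk | Coordinator (7.1.1) | Not named; required by Table 1 and 10.4.11 | Not provided for |

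The 3-month paragraph of 7.1.1 names weight, blood pressure, SF-12, SAQ-7, ADLs and PHQ-8 as repeated instruments and leaves frailty out. Section 7.2.4 refers back to Table 1, which names no assessor.

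**2. Inference.** Frailty must be measured at 3 months. The only person to whom the documents ever assign it is the coordinator. The blinded person's named tasks at that visit are the 6MWT and GAS, and nobody else is blinded. The natural reading is that the coordinator measures grip and gait knowing the arm. This is inferred, not stated.

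**3. Dependence of the classification on the two tests.** Frail means at least 3 of 5 criteria.
- Exactly three criteria: C(5,3) = 10 possible profiles. Only C(3,3) = 1 contains neither grip nor gait, so 10 − 1 = 9 contain at least one. In those nine, one of these items crossing its cut-off is enough to leave frailty.
- Exactly four criteria: C(5,4) = 5 profiles. Leaving frailty through these tests alone needs both to cross, which is possible in the C(3,2) = 3 profiles that contain both.
- All five criteria: losing both leaves 5 − 2 = 3, which is still frail.

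This counts routes, not probabilities, because the profiles are not equally common.

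**4. Size.** A bias in the transition rate would need the number frail at baseline, the share close to the grip or gait cut-off, and the effect of encouragement. The documents give none of these, so no size can be computed.

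**5. Four items or five.** If a site scored only the four items in 7.1.1, someone with exactly three criteria, one of them low physical activity, would score 2 and be classed not frail. That covers C(4,2) = 6 of the 10 three-criterion profiles. Section 7.2.2, the checklist for the same baseline visit, does list the fifth item, so this is a text to reconcile and not evidence of mis-scoring.

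**The case against.** The case against has five parts.

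- **The assessor is inferred.** The coordinator block in 7.1.1 describes baseline, when there is no arm to know. A reader might infer that the plan expressly gives the 3-month tests to an unblinded coordinator. It does not; it is silent. This stands and limits the claim, but the silence is itself a reason to amend.
- **It is a disclosed design choice.** The trial is open-label with blinded assessment of the primary endpoint, and frailty is ancillary and absent from the power table in 10.5. That limits the importance. It does not explain the gap, because 7.2.4 already extends blinding to GAS, a secondary endpoint, in order to reduce bias.
- **Grip and gait may be less open to coaching than the 6MWT.** The protocol does not call them effort tests or say whether the short walk is at usual or fast pace. The worry about "no differential encouragement in the intervention arm" is written for the 6MWT only. So equal susceptibility cannot be claimed, only exposure to the same mechanism. Section 7.1.1 does say that coordinator procedures use standardized instruments, but the 6MWT also follows standardized recommendations and was still blinded.
- **A frailty result would not be beyond checking.** A reader might infer that a positive result could not be told apart from tester encouragement. That is too strong. Only two criteria are in question, results by component would show whether transitions came through them, and the blinded 6-minute walk distance gives related evidence on function.
- **Recruitment has begun.** Section 4.1 refers to paused enrollment at one site, so a change now could mix two measurement procedures. This is fair, and the fix allows for it.

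**Conclusion.** The point holds as a low-cost improvement to an ancillary endpoint. As the plan stands, two of the five frailty criteria appear to be measured at 3 months by someone who knows the arm, with no safeguard of the kind given to the 6MWT. Any effect would enter at follow-up only, and would favour the intervention if encouragement were greater in that arm. The primary 6-minute walk comparison is unaffected.

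This rests on two assumptions: that the coordinator who measures frailty at baseline also does so at 3 months, and that grip and the short walk respond to some degree to encouragement.

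A reader might be tempted to put a number on the bias. For example, assume that 15% of the 240 evaluable intervention participants are frail (36) and that coaching tips four of them over a cut-off: 4/36 = 11 percentage points. The documents support neither the 15% nor the four, so that figure should not be used. The four-versus-five item mismatch is a separate editorial matter.

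**What to change.** 1. In 7.1.1 and 7.2.4, assign grip strength and the 15-foot walk at the 3-month visit to the blinded assessor who already attends for the 6MWT and GAS.
2. Specify that both are done **before** the 6MWT. Section 7.1.1 places the 6MWT after the coordinator's assessments at baseline. Testing after the walk only at follow-up would compare rested with possibly fatigued measurements.
3. Leave the self-report items with the coordinator. Participants know their arm, so a blinded interviewer would not make those answers blinded.
4. As recruitment has begun, record on the frailty form who took the two measurements and whether that person was blinded, so that results before and after the change can be shown separately.
5. Add low physical activity to the frailty list in 7.1.1, to agree with 4.2.3, 7.2.2 and 10.4.11, and name frailty among the repeated measures in the 3-month paragraph.

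The cost is a few minutes of the blinded assessor's time per 3-month visit, one extra form entry and a text amendment. No new staff, test or visit is needed.

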7.1.2 Standard of Care Study Procedures

Both intervention and control arms will also receive a referral to (but not required attendance at) traditional ambulatory CR, which is the current standard of care. At NYU, Bellevue, UMass and Yale, the typical first visit for traditional CR occurs within 4 weeks of discharge.

7.2 Study Schedule

7.2.1 Screening

Inclusion and exclusion criteria will be determined through screening of the EHR.

Screening (1-5 days prior to enrollment, Day -5 to Day -1)

- A daily list is generated by EPIC based on diagnostic test results (inpatients with AMI) or the cardiac catheterization lab schedule (outpatients going for elective coronary angiography) from the time of last update (generally last 24 hours during the week except Monday, which captures last 72 hours inclusive of Friday and weekend admissions).
- A second list is generated daily by EPIC based on outpatient cardiology appointment schedules to capture participants' appointments with his/her respective cardiologist.

CONFIDENTIAL

- The staff screen the list of patients and sends potentially eligible patients to the Principal Investigator for review.
- The PI (at NYU Tisch and Bellevue sites) will be responsible for reviewing the list of eligible patients and whether inclusion/exclusion criteria are met.
- For those deemed eligible, the staff will send an email to the treating clinician informing the clinician that the research coordinator will approach the patient for participation in the research study.
- If amenable to approach, RC will approach to enroll subject.
- If the research coordinator questions the capacity to self-consent, decisional impairment will be formally assessed by the using the University of California, San Diego Brief Assessment of Capacity to Consent (UBACC).

At the NYU-Winthrop location, [name] and [name] (sub-investigators) will be responsible at the location for reviewing and confirming eligible patients identified by the NYU-Winthrop research coordinator. At the UMMHC site, [name] (site PI) will be responsible at the UMMHC site for reviewing and confirming eligible patients identified by the UMMHC research coordinator. At the Yale site, [name] (site PI) will be responsible at the Yale site for reviewing and confirming eligible patients identified by the Yale research coordinator.

7.2.2 Enrollment/Baseline

Enrollment/Baseline Visit (Visit 1, Day 1)

- Obtain informed consent of potential participant verified by signature on study informed consent form.
- Verify inclusion/exclusion criteria.
- Obtain demographic information, medical history, medication history, comorbidities, and laboratory/cardiac test results.
- Obtain height and weight.
- Record blood pressure.
- Administer study assessments:
 - 6-minute walk test. Standard protocol including vital signs measurement pre- and post-testing.
 - Frailty elements: Unintentional weight loss (≥ 10 pounds in past 1 year), weak grip strength (measured by handheld dynamometer), exhaustion (measured by two questions from CES-D scale), slow gait (measured in meters/second over a 15-foot walk), and low physical activity (measured by kilocalories per week expended).
- Conduct questionnaires:
 - SF-12
 - SAQ-7
 - ADLs
 - Mini-Cog
 - PHQ-8
 - GAS
- (Intervention Participants only):
 - Provide participants with tablet computer
 - Receive FitBit wearable activity monitor and BP cuff monitor
 - Education on cardiac risk factor management (in person or remote)
 - Ascertainment of home environment and barriers to mobility (in person or remote)
 - Introduction to the mHealth-CR software
 - Personalized exercise plan: Participants will be instructed by the exercise therapist to use mHealth-CR for at least 5/7 days each week. Training will include education on BP cuff use.
- All participants will be instructed to participate in phone calls with the research coordinator to complete ADL assessments.

CONFIDENTIAL

This material is the property of the NYU School of Medicine and Langone Medical Center. Do not disclose or use except as authorized in writing by the study sponsor

7.2.3 Intermediate Visits

7.2.3.1 Home activities (Day 2-89)

- (All participants): Record all participants' Activities of Daily Living Assessment data once every two weeks during the first month, and then monthly during months 2 and 3 (+ 5 days post due date).
- (Intervention Participants only): Record participants' adherence to mHealth-CR program from Moving Analytics and FitBit platform
 - Daily therapist-directed activity (walking, jogging, etc.)
 - Weekly video education
 - FitBit tracking and review of steps
 - Daily mHealth data entry
- Record participants' weekly blood pressure data.
- Administer weekly therapist phone calls for counseling/activity review (+ 5 days post due date).
- Record adverse events as reported by participant or observed by investigator.

